Primary Attack Rate	The proportion of first-order contacts of the index case who themselves go on to be diagnosed with COVID-19
Secondary Attack Rate	The proportion of second-order contacts of the index case who themselves go on to be diagnosed with COVID-19

Figure 1: Definitions used for the chain of transmission

1. Rationale

When a person in a school / FE college¹ is diagnosed with COVID-19, first-order close contacts are required to self-isolate for 10 days. In schools, some groups of these close contacts (often managed as 'bubbles') may be quite large (e.g. a whole year group of over 250 pupils) and self-isolation has negative impacts on the education, psychological health and wellbeing of those affected². There is some evidence that suggests that compliance with self-isolation outside the school setting may be as low as 11% in asymptomatic contacts³ (although this may have improved since self-isolation has become a legal requirement). Modelling data shows daily testing of first-order contacts, using rapid lateral flow tests, could avert a similar level of onward virus transmission as self-isolation. In addition, recent work, has found that contacts identified by Test and Trace in the same household are more likely to become infected than first-order contacts at work, school or elsewhere. Primary age children are less likely to infect someone else and contact in schools with an infected child and are at a lower risk of transmission⁴.

It is proposed that when a positive case is detected, first-order close contacts will be offered the choice of being tested daily using rapid Lateral Flow Device antigen testing as an alternative to the requirement to self-isolate. A first-order contact with a negative test at the start of the school day can remain in school. However, they will be advised to self-isolate outside school. A person who tests positive with LFD will follow national protocols and self-isolate for ten days. This process is referred to here as Daily Contact Testing (DCT). DCT will enable the pupil's education to continue and reduced the health and wellbeing impacts of self-isolation.

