3.2 Methods

3.1 Overview of Design

This is a pragmatic cluster randomised controlled study. Eligible participating schools will be stratified according to institution type, size, Free School Meal prevalence and local COVID-19 prevalence and randomly allocated into the two study arms. A schematic summarising the study design and participant sub-groups can be found in Figure 2 below.

Regular Active Case Finding. In schools participating in either arm of the study, consent will be obtained from adults/parents/guardians for voluntary weekly testing of all students and biweekly testing of all staff⁵. Tests will be performed with lateral flow devices (LFD)*, and results will be reported in the NHS Test and Trace database. LFD Tests will initially be performed as an assisted test in a school setting. Once a reliable protocol for home testing and recording of LFD is available, schools will be offered the option for at-home self-testing for weekly case finding.

Individuals who test positive will self-isolate and identify first-order contacts according to national guidelines. In addition, symptomatic cases who test positive via NHS Test and Trace, and asymptomatic cases who test positive outside the in-school testing regimen will self-isolate and report their results to the school. All individuals with a positive test will be asked to provide a PCR swab test for genomic sequencing.

1. Intervention (Daily Contact Testing) Arm

a. Public Health Intervention: Consenting first-order contacts of a COVID-positive index case will receive daily contact testing for 7 days from the point of being notified they are a close contact⁶. This will consist of a daily LFD*. Those that receive a negative LFD result can attend school for that day, but other than travelling to and from school will be instructed to continue to self-isolate outside the school setting. Those that receive a positive LFD result should not attend school and will be instructed to self-isolate for 10 days according to national guidelines. The contacts of all first-order contacts (i.e. 'second-order contacts') will be identified to allow the determination of secondary attack rate.

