3.7 Identification of Second-Order Contacts

As discussed above, the rate of COVID-19 positivity in the second-order contacts of index cases (i.e. the contacts of first-order contacts) will be an endpoint used to assess the public health effectiveness of DCT for school populations. Several methods will be used to identify the second-order contacts of index cases:

• In-school secondary contacts: As part of their existing COVID-19 management policy schools are required to segment their population into distinct 'bubbles' (e.g., year group), membership of which is unique. Members of one bubble should not be interacting with members of another. As a result, all the contacts of a member of a specific bubble should also be members of the same bubble.

In the event of a positive index case within a bubble, the school will identify those bubble members it considers to be close contacts of the index case (this will often not be the entire bubble). These close contacts (i.e. 'first-order contacts' in the context of this study) are subject to self-isolation or DCT depending on their arm.

All other members of the index case's bubble will be considered second-order contacts for the purposes of this study. Membership of each bubble will be provided by participating schools at the start of the study, and should not vary during the study.

• Household contacts of first-order contacts: Another group of second-order contacts are individuals who live in the same household as a first-order contact. These may attend the same school or may not. These individuals will be 'identified' by querying routinely collected NHS Test and Trace testing data for individuals with the same residential address as any first-order contact. The method to identify household contacts will only identify household contacts who are in Test and Trace systems.

Within the scope of this study we do not intend (for operational reasons) to identify non-school, nonhousehold contacts of first-order contacts. As first-order contacts are required to maintain selfisolation outside the school environment (even if they are undertaking DCT) this group should be minimal in size. However, it is an acknowledged limitation of the study. We also do not intend (for similar reasons) to identify individuals within the school who are not a member of the same bubble as a first-order contact but have had close contact with them. We acknowledge this as another limitation of the study.

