3.8 Assessment of Behavioural and Other Outcomes

Assessment of the behavioural components of the evaluation framework will include the following:

- 1. Survey of a) self-reported out of school activities and contacts (for comparison in testnegative, test-positive and self-isolating participants); b) views of testing (compared with selfisolation)
- 2. PPI input and qualitative research to understand views and experiences of and responses to testing of pupils, parents and school staff teachers and others

Participants in both the Interventional and Control Arms will be invited to complete a very brief online survey; this will include all participants who are a first-order contact of a positive index case. Measurement will be on day 7 after notification of being the contact⁷, using self-report measures of social contacts and other behaviours adapted from measures already in use. To promote honest self-reporting, an anonymous survey instrument will be used (as in the previous 'Agile Lighthouse' evaluation of DCT), which can be found in Appendix 2.

Outcome 2 focuses on gathering the perceptions, experiences and beliefs of those involved in the testing process, including pupils, parents, teachers and administrators. In collecting this data, it is crucial that the burden on teachers and school staff is reduced as far as possible during what is already an extremely challenging time for them. We have explored the potential for using existing research vehicles (e.g. the Pupil and Parent Panel omnibus survey), but these would not allow us to deliver the objectives of the present study. The bespoke data collections have therefore been streamlined to lower burden. The approaches that will be used are:

- User research carried out in two waves within both Phase 1 and Phase 2:
 - Wave 1: At the beginning of the testing period to explore the practicalities of delivering the protocol within the 'intervention arm' schools. This will be no more than ten interviews (anticipated approx. 20-30 minutes, no more than 1 participant per school site) with school staff (teachers and non-teachers) involved in management/implementation focusing on the process and expectations for the testing. Data will enable a view of the study implementation (allowing adjustments to be made if required) as well as the feasibility of wider rollout.

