4.2.1 Interventional (Daily Contact Testing) Arm

All those in the same first-order close contact group as the positive case will be offered the option of being tested by LFD at the start of every school day, until day 7 after being notified of being a contact¹¹. Those who do not consent to daily testing will be subject to the process outlined in Section 4.4. LFD antigen testing will be via one of two delivery models:

- 1. Supervised anterior nares swabbing, with device use assisted within a school's ATS model. The workforce for this will be trained according to national NHS T&T standard process.
- 2. Once a suitable protocol is available, at-home self-anterior nares self-swabbing under supervision of the parent / guardian (in alignment with national NHS T&T guidance). Swab samples will be self-applied at home to the LFD device and the result self-read by students under supervision of the parent / guardian, or by the parent / guardian if the student does not feel confident to use the device themselves.¹²

Those that test **negative** on the LFD negative at the start of the school day will be allowed to attend school for that day until their next test is due. It will not allow them to avoid self-isolation outside the school setting, and this will be communicated to participants using accessible, standardised materials drawing on behaviour change techniques and developed with user feedback to ensure they are credible and motivating. Participants will be required to self-isolate on days where a test has not been performed (e.g. weekends). If a non-tested day occurs at the end of Daily Contact Testing, a further negative test will be required to complete and release from the Daily Contact Testing protocol.

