A new option is to carry out daily tests for up to 7 days, which means that every day you have a negative test you can carry on with your normal activities and do not need to self-isolate.

Which option do you prefer?

- Strongly prefer 10 day self-isolation option
- Somewhat prefer 10 day self-isolation option
- No preference for either option
- Somewhat prefer daily testing option
- Strongly prefer daily testing option

4. Demographics

What school do you attend?

How old are you?

What is your gender?

- Male
- Female
- Prefer to self-describe
- Prefer not to say

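### The survey's preference question describes a freer daily testing option than the one the trial delivers

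*Protocol*

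**What the plan says.** Part 3 of the Appendix 2 survey sets usual self-isolation at home for 10 days against a new option of daily tests for up to 7 days. It explains that under the new option, "every day you have a negative test you can carry on with your normal activities and do not need to self-isolate". A five-point preference scale follows.

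The body of the protocol describes daily contact testing (DCT) differently:

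- Section 1 (Rationale), on contacts who test negative and stay in school: "they will be advised to self-isolate outside school".
- Section 3.1, on contacts with a negative result: "other than travelling to and from school will be instructed to continue to self-isolate outside the school setting".
- Section 3.7: "first-order contacts are required to maintain selfisolation outside the school environment (even if they are undertaking DCT").
- Section 4.2.1, on what a negative test permits: "It will not allow them to avoid self-isolation outside the school setting".
- Section 4.2.1, on untested days: "Participants will be required to self-isolate on days where a test has not been performed (e.g. weekends").

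Section 3.8 gives the survey's purpose as including "views of testing (compared with selfisolation"), and its audience: "Participants in both the Interventional and Control Arms will be invited to complete a very brief online survey". It is completed on day 7 after notification.

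**The concern.** A stated preference can be interpreted only if both options are described as they are. Here 10-day isolation is put plainly, while daily testing is described as lifting isolation altogether on any day with a negative test. A respondent who chooses daily testing may be choosing the freedom to see friends or go out, which the trial's DCT does not give.

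What is at stake is the section 3.8 outcome on views of testing. The section 3.6 list of secondary endpoints also includes behavioural outcomes such as acceptability and self-reported perceptions. If the result is read as support for DCT as trialled, that support is likely to be overstated. A further difficulty is that an official study document tells intervention contacts something at odds with their instructions, at a time when some may still be bound by them.

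**Working it through.** No sample size, power or error rate is involved, so the check is a comparison of texts and a count of items.

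**Step 1: compare the option described with the option delivered.**

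| After a negative test | Appendix 2, part 3 | Sections 1, 3.1, 3.7, 4.2.1 |
|---|---|---|
| Attend school | Yes | Yes |
| Other activities outside the home | Yes | No, apart from travel to and from school |
| Self-isolation outside school | Not needed | Continues |
| Untested days | Not mentioned | Isolate (section 4.2.1) |

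The second and third rows are contradictions, and in both the survey is the more permissive side. The last row is an omission: the item speaks only of days with a negative test, so it does not contradict the rule for untested days.

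**Step 2: look for a reconciling text.** None says that the item describes a future or hypothetical policy, or that it supersedes the regimen.

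**Step 3: count the items affected.** Appendix 2 contains:

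- part 1: recent activities (behaviour);
- item 2a: test history;
- item 2b: confidence in the accuracy of results, restricted to the DCT group;
- part 3: the preference item, with no restriction by arm;
- part 4: demographics.

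Items on views of testing are therefore 2b and part 3 for the DCT group (1 of 2 misdescribed) and part 3 alone for control contacts (1 of 1 misdescribed).

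**Step 4: consider direction by arm.** Making one option look less restrictive should move answers towards it. Section 4.2.1 commits to telling intervention contacts the real rule through standardised materials, and those who take up DCT live under it. Control contacts have no experience of DCT within the trial. The shift is therefore likely to be larger in the control arm, and a between-arm difference in preference could partly reflect different understanding of the option. This is reasoning and not a calculation.

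**The case against.** The strongest reply is that this is one loose sentence in a short behavioural survey, and that the protocol uses similar shorthand itself. The Arm 2 summary in section 2.1 confines self-isolation to those who test positive, and section 1 presents daily testing as an alternative to having to isolate. Those lines are summaries, however. Section 1 goes on to add the restriction outside school, and the sections that define the regimen all state it. Neither summary says that contacts may resume normal activities.

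Second, the control-arm argument depends on information sheets that are not shown; control contacts may already know the school-only rule. This stands as a limit on the direction and its split by arm, which remain inferences. It does not touch the contradiction.

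Third, the survey asks for the respondent's school, so answers can be split by arm, and they can be reported alongside the exact wording used. Both steps limit the harm, but neither recovers what respondents would have said to a true description.

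Fourth, the Appendix 7.2 interviews cover preference, including among control contacts. They are useful context, but the protocol says that they are not meant to be generalisable, so they cannot replace the survey measure.

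Last, the replacement wording proposed here leaves out the return to Day 0 after a further positive case and the extra exit test when the period ends on an untested day. That is true. A short item need not carry every rule, and these omissions do not make the wording wrong.

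**Conclusion.** The concern holds. The preference item contradicts the regimen on what a negative test permits, and as written it elicits preference for an option the trial does not deliver. Confidence is high on the contradiction, which rests only on the protocol's text. The direction (towards daily testing, mainly among control contacts) is inferred, and the size of the shift on the five-point scale cannot be derived.

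The reach is narrow. The co-primary endpoints, the numbered endpoints of section 2.1 (including actual uptake of DCT) and the behaviour items do not depend on this sentence. It should be corrected because the error is clear, avoidable and cannot be repaired by analysis after collection. It does not threaten the trial's main conclusions.

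**What to change.** Before the survey is fielded, replace the description of the daily testing option with wording such as:

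> A new option is to take a test each school day for 7 days. If your test is negative you can go to school that day, but you must still self-isolate outside school and on days without a test.

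The refinement of materials in Phase 1 (section 3.12) is a natural point for the change. Any responses already collected under the present wording should be reported separately. Optionally, use the same description in the Appendix 7.2 interview questions for self-isolating and control contacts, where testing and isolating are joined by a slash and the meaning is ambiguous.

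The cost is rewording one survey sentence and notifying the ethics body.

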Appendix 3 – Terms of Reference for Independent Trial Steering Group (TSC)

The role of the TSC

The role of the TSC is to provide overall supervision for the trial to ensure that the project is conducted to the rigorous standards set out in the Department of Health and Social Care's Research Governance Framework for Health and Social Care and the Guidelines for Good Clinical Practice. It should be noted that the day-to-day management of the project is the responsibility of the Principal Investigator, and as such the Principal Investigator may wish to set up a separate Project Management Group (PMG) to assist with this function.

The main features of the TSC are as follows:

- To provide advice, through its Chair, to The Department for Education, the Department for Health and Social Care and the Chief Investigator on all appropriate aspects of the trial
- To concentrate on progress of the trial, adherence to the protocol, patient safety (where appropriate) and the consideration of new information of relevance to the research question
- The rights, safety and well-being of the participants are the most important considerations and should prevail over the interests of science and society
- To ensure appropriate ethical and other approvals are obtained in line with the project plan
- To agree proposals for substantial protocol amendments and provide advice regarding approvals of such amendments
- To provide advice to the investigators on all aspects of the trial.

Constitution of the TSC

- The members of the TSG will be appointed by the Department of Health and Social Care and the Department for Education
- Independent * members must make up a minimum of 75% of the TSC membership.
- The minimum quorum for any TSC meeting to conduct business is 67% (two thirds) of the appointed membership.
- Only appointed members will be entitled to vote, and the Chair will have a casting vote
- The Chair and members must sign and maintain a log of potential conflicts and/or interests
- Attendance at TSC meetings by non-members is at the discretion of the Chair
- The primary TSC reporting line is via the Chair to the Department of Health and Social Care and the Department for Education

* Independence is defined as follows:

- Not part of the same institution as any of the applicants or members of the project team. This means holding neither a substantive nor honorary contract with said institution.
- Not related to any of the applicants or project team members.

- For the Chair only; not an applicant on a rival proposal.
- It is recognised that independence status may change during the duration of the trial.

Composition Requirements of the TSC

- An Independent* Chair
- An Independent* statistician
- At least one PPI member
- Others with expertise relevant to the project, such as an infectious disease epidemiologist and an expert in running studies in educational settings
- The TSC may invite observers to meetings

TSC meetings

- The TSC should meet at least monthly
- TSC meetings should be scheduled to follow shortly after IDMC meetings so that reports from that group can be considered if appropriate
- Minutes of meetings should be sent to all members, the Department of Health and Social Care, the Department for Education and the Principal Investigator and be retained in the study master file.

The responsibility for calling and organising TSC meetings lies with the Principal Investigator, in association with the Chair.

The Role of the Chair of TSC

The Chair's responsibilities include:

- Liaising with the Principal Investigator to arrange a meeting to finalise the protocol and to set up a schedule of meetings to align with the project plan
- Establishing clear reporting lines.
- Being familiar with relevant guidance documents and with the role of the IDMC if appropriate.
- Providing an independent*, experienced opinion if conflicts arise between the needs of the research team, the participating organisations and/or any other agencies
- Leading the TSC to provide regular, impartial oversight of the study, especially to identify and pre-empt problems
- Ensuring that changes to the protocol are debated and endorsed by the TSC;
- Being available to provide independent* advice as required, not just when TSC meetings are scheduled

• Commenting in detail (when appropriate) regarding the continuation, extension or termination of the project. NB: The TSC Chair does not need to be a content expert him/herself but needs to ensure that enough content expertise is available for the group to perform its oversight function effectively.

Appendix 4 – Terms of Reference for Independent Data Monitoring Committee (IDMC)

The role of the IDMC

The IDMC's main role is as follows:

- It is the only body involved in the trial that has access to the unblinded comparative data
- The role of its members is to monitor these data and make recommendations to the Trial Steering Committee (TSC) on whether there is there evidence beyond reasonable doubt that one arm is superior to another arm such that it is likely to change public health or educational practice.
- The safety, rights and well-being of the trial participants are paramount
- The IDMC considers the need for any interim analysis advising the TSC regarding the release of data and/or information
- The IDMC may be asked by the ISSG to consider data emerging from other related studies
- There are also rare occasions when the IDMC chair might be asked, by the chair of the TSC to provide advice based on a confidential interim or futility analysis if serious concerns are raised about the viability of the study or if the research team are requesting significant extensions.
- Criteria should be agreed at which continuation of the trial is considered futile and the DM(E)C would only indicate if these had been passed or not as this would limit the potential for un-blinding.

Constitution of the IDMC

- Members of the IDMC will be appointed by the Department of Health and Social Care and the Department for Education
- Only appointed members will be entitled to vote, and the Chair will have a casting vote
- The minimum quoracy for a meeting to conduct business is 67% (two thirds) of appointed members
- The Chair and members must sign and maintain a log of potential conflicts and/or interests
- Attendance at IDMC meetings by non-members is at the discretion of the Chair
- The primary IDMC reporting line is via the Chair to the TSC.

Composition Requirements of the IDMC

- All IDMC members are to be independent*
- Membership of the IDMC will be four members, comprising experts in the field, e.g. a clinician with experience in infectious disease epidemiology, an expert in working with educational settings and an expert trial statistician.
IDMC Meetings

- Responsibility for calling and organising IDMC meetings lies with the Principal Investigator, in association with the Chair of the IDMC. The project team should provide the IDMC with support for organising and minuting meetings and a comprehensive report, the content of which should be agreed in advance by the Chair of the DMC.
- The IDMC should be presented with an interim analysis of the trial data prior to the return of the majority of pupils to school.
- The IDMC should determine their meeting frequency, but must meet to consider the interim analysis before the full return of pupils to school.
- Minutes of meeting should be sent to all members, DfE, DHSC, the TSC and the study master file. It should be noted that the minutes may have 'in camera' items redacted from some copies.

*Independence is defined as follows:

- Not part of the same institution as any of the applicants or members of the project team. This means holding neither a substantive nor honorary contract with said institution.
- Not related to any of the applicants or project team members.
- For the Chair only; not an applicant on a rival proposal.
- It is recognised that independence status may change during the duration of the trial.

